**2. Background**

The WHI was one of the largest studies on the health of postmenopausal women done to date. Between 1993 and 1998, more than 161,000 women between 50 and 79 years of age joined the WHI which consisted of an Observational Study (OS) involving 93,676 women and a partial factorial Clinical Trial (CT) consisting of three components: a Dietary Modification Trial (DM) with 48,835 participants; a Hormone Replacement Trial (HT) with 27,347 participants, which included an Estrogen plus Progestin (E+P) arm (16,608 participants) and an Estrogen-alone (E-alone) arm (10,739 participants); and a Calcium and Vitamin D Supplement Trial (CaD) with 36,282 participants.

The original protocol indicated that study close-out was to occur between October 2004 and March 2005. Participants in the DM and CaD trials remained on intervention until their last clinic visits during this interval. The E+P intervention was terminated in July 2002 at the recommendation of the WHI Data and Safety Monitoring Board, following the findings that risks outweighed the benefits for combined hormone use (The Writing Group for the Women’s Health Initiative, 2002). The E-alone intervention was stopped in March 2004 at the direction of the NHLBI based on an increased risk of stroke and the unlikelihood of being able to establish either CHD benefit or an adverse effect on breast cancer (The Women’s Health Initiative Steering Committee, 2004). Participants in both hormone trials continued to be followed, including annual mammography, through the scheduled close-out visits. Participants in the OS were followed annually by mail until the final cycle of mailings that began in spring of 2004. Details on the design of the WHI, WHI participants, and major study findings for the DM and CaD are described elsewhere (The Women’s Health Initiative Study Group, 1998; Anderson et al, 2003, Prentice et al, 2006a, Beresford et al, 2006, Jackson et al, 2006, Wactawski-Wende et al, 2006; Howard et al, 2006).

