The ability to estimate relative risks reliably for the outcomes of interest in the WHI as a function of baseline characteristics (exposures, behaviors or biologic measurements), or as a function of changes in such characteristics between baseline and one or three years is dependent on the accurate measurement of the characteristics (and outcomes) under study, and the accurate ascertainment and proper accommodation of all pertinent confounding factors. Even measurement error that is nondifferential in the sense that it is unrelated to disease risk given the 'true' characteristic values, can severely attenuate or otherwise distort relative risk estimates. Since many of the characteristics ascertained (e.g., blood analytes, nutrient intakes, blood cholesterol) are subject to noteworthy measurement error, a stratified 1% random subsample of the OS women had repeat baseline information and specimens obtained at between one and three months following their OS enrollment, and again at between one and three months following their three year clinic visit. This reliability subsample provides information of the reproducibility of the measurements taken (Langer et al, 2003), and can be used, under classical measurement error assumptions, to correct relative risk estimates for non-differential error in predictor and confounding variables. The 1% reliability sample was stratified on age, racial/ethnic group, and socioeconomic group. The size of the WHI study population, and the comprehensive set of measurements obtained allow a particularly thorough accommodation of confounding, by means of individual matching, stratification or regression modeling. Since, the measurement properties of some exposures of interest (e.g., self-reported nutrient consumption; self-reported physical activity patterns) involve more measurement error properties that are more complex than those acknowledged by the classical measurement model, including important systematic biases, WHI investigators have carried out nutrition and physical activity biomarker studies in subsets of WHI cohorts. These biomarker sub-studies have potential to yield calibrated exposures throughout WHI cohorts for some nutrients and for activity-related energy expenditure. Results using this calibration approach have begun to be published (Neuhouser et al, 2008; Prentice et al, 2009) and several other applications are underway. The WHI is in a unique position to lead a new cycle of more reliable association studies in the important diet, physical activity, and energy balance areas of epidemiology, during upcoming years.

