Analyses of intervention effects will typically be stratified on baseline age (50-54, 55-59, 60-69, 70-79), and self-reported prevalent disease (if applicable) for that outcome, and the categories of the other interventions. The primary HT comparisons will be examined separately based on baseline WHI hysterectomy status.

To assess potential selection bias among Extension Study participants relative to the initial trial cohort, comparisons of demographics, health history, adherence to intervention and key outcome event rates will be made between Extension Study enrollees and non-enrollees using data from the initial WHI database. If an assumption of no selection bias is supported, women who did not consent to the Extension Study will be censored at their last follow-up contact during the original WHI study, except for total mortality analyses where vital status information will be obtained from the NDI. Methods to account for non-representative enrollment using inverse sampling probability weighted tests may be employed if there is evidence of noteworthy selection in Extension Study enrollment.

All analyses of clinical trial results will be reported as two-sided tests with acknowledgement of multiple testing issues, either by appropriate adjustment of p-values and confidence intervals or by an acknowledgement of the number of tests performed.

More detailed explanatory analyses will include tests for group differences with concomitant adjustment for covariates, as well as explanatory analyses that examine the extent to which an intervention benefit can be explained by changes in intermediate variables and outcomes (e.g., nutritional and biochemical measurements). These analyses will be conducted using relative risk regression methods, with appropriate account of measurement error in the intermediate variable measurements as necessary, using data obtained in the aforementioned reliability sub-study. Nested case-control and case-cohort sampling procedures (see next subsection) will be used in most such analyses since stored materials used to determine immediate variable values will not be routinely analyzed for the entire CT cohort.

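### For self-reported dietary mediators, the only correction data section 7.5 names are OS replicates, tied to an error model that section 7.4 calls inadequate for self-reported intake

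*Protocol*

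**What the plan says.** Section 7.5 follows the intention-to-treat comparisons with explanatory analyses of the extent to which an intervention benefit "can be explained by changes in intermediate variables and outcomes (e.g., nutritional and biochemical measurements"). These use relative risk regression, "with appropriate account of measurement error in the intermediate variable measurements as necessary", and the data source is fixed: "using data obtained in the aforementioned reliability sub-study". Section 7.5 names no other source.

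The only study that fits is in section 7.4, where "a stratified 1% random subsample of the OS women had repeat baseline information and specimens obtained" one to three months after enrollment and again one to three months after the three-year visit. Section 2 gives an "Observational Study (OS) involving 93,676 women". Section 7.4 says this sample can correct relative risks for non-differential error if the error is classical, and it lists nutrient intakes among the measurements that motivated the sample.

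Later in the same paragraph, section 7.4 says that some exposures, with self-reported nutrient consumption and physical activity as examples, have error properties "more complex than those acknowledged by the classical measurement model, including important systematic biases". For that reason biomarker sub-studies were run in subsets of the WHI cohorts. They may give calibrated values for some nutrients and for activity-related energy expenditure. Section 7.5 does not mention them.

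Section 7.5 also says that most of these analyses will use nested case-control or case-cohort sampling, because "stored materials used to determine immediate variable values will not be routinely analyzed for the entire CT cohort".

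**The concern.** The two sections do not fit together for one class of mediator. Section 7.4 recognises that replicates are not enough for self-reported intake and describes a better source. Section 7.5 keeps nutritional mediators in scope but points only to the replicates.

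Replicates reveal the error that differs between a woman's repeated reports. They do not reveal error common to all her reports, or error that depends on randomized arm. The second kind is a real possibility here: section 2 says the Dietary Modification (DM) intervention taught dietary behaviors and that newsletters later promoted keeping them up. Women taught a diet may change how they report as well as how they eat. OS women were not randomized, so their replicates carry no information on this.

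At stake is how a DM benefit is interpreted. A share explained that has been corrected for measurement error looks more trustworthy than an uncorrected one, yet it may still contain the biases that section 7.4 warns about. Section 7.4 itself says that careful handling of measurement error matters particularly when changes in risk factors are analysed, and section 7.5 analyses changes.

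**Working it through.** The Protocol states no figure to reproduce and gives no error variances. The check is therefore of which errors the named data can identify, with assumed values to show how the result behaves.

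**Inputs from the Protocol.** The OS has 93,676 women (section 2), and 0.01 × 93,676 = 936.76, about 937 women, none of them randomized in the CT. Repeats are near baseline and near year 3 (section 7.4). The mediators are changes (section 7.5).

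**Model.** Let D be the self-reported change in the mediator:

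D = b·ΔT + g·a·X + d + e

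Here ΔT is the true change (within-arm variance 1), X the arm, a the true between-arm difference in change, b a scaling bias, g the arm-dependent reporting shift as a fraction of a, d a person-specific drift in bias between the two times (variance v), and e random error (variance w).

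**Result.**
- Within arm, the regression on D returns b/(b² + v + w) of the true coefficient.
- The OS replicates give a reliability of (b² + v)/(b² + v + w). Dividing by it leaves b/(b² + v).
- The reported between-arm change is (b + g) times the true one.
- So estimated share / true share = b(b + g)/(b² + v).

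Random error w drops out, so the correction does its intended job. The terms b, g and v remain, and the replicates identify none of them.

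**Values (all assumed).**

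| b | v | g | estimated / true share |
|---|---|---|---|
| 1 | 0 | 0 | 1.00 |
| 1 | 0 | -0.25 | 0.75 |
| 1 | 0 | +0.25 | 1.25 |
| 1 | 0 | +0.50 | 1.50 |
| 1 | 0.5 | 0 | 0.67 |
| 1 | 0.5 | +0.50 | 1.00 |

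Over b of 1 or 0.7, v from 0 to 1 and g from -0.25 to 0.5, the extremes are 0.7 × 0.45/1.49 = 0.21 and 0.7 × 1.2/0.49 = 1.71.

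A simulation of this algebra (400,000 women, linear approximation to the log relative risk, w = 0.5, true share 0.50) gave 0.495 with classical error, 0.753 with g = 0.5, 0.336 with v = 0.5, and 0.500 with both. These match the rows with ratios 1.00, 1.50, 0.67 and 1.00.

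**The case against.** The strongest reply is that section 7.5 prescribes no classical model. It asks for an appropriate account of error where needed, and the choice of model for each mediator can be left to an analysis plan. This is right about the model. It does not settle the data source, which section 7.5 does name: OS replicates alone cannot identify shared or arm-dependent reporting bias under any model.

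Second, section 7.5 never says that the nutritional mediators are self-reported, and it expects stored materials in most of these analyses. Nutritional measurements can be blood concentrations, and the sub-study repeated specimens too. This stands and limits the scope. A reader might infer that all the CT mediation analyses are compromised. The Protocol does not support that, since replicate correction can be reasonable for assayed analytes.

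Third, a reader might infer a definite attenuation. If each woman carried a constant bias and follow-up *levels* were modelled, the corrected coefficient would be 1/(1 + v) of its true value, with v now the variance of that constant bias: 0.67 at v = 0.5 and 0.50 at v = 1.0. But section 7.5 analyses *changes*, and a constant additive bias cancels in a within-person difference. What remains is drifting or arm-dependent error (and any scaling bias), whose size is not stated.

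Fourth, these are explanatory analyses, and the DM trial's effects are not among the four primary objectives in section 3. That lowers the importance but does not remove the mismatch.

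**Conclusion.** The point holds for self-reported dietary mediators only. For these, section 7.5 names a single correction source that section 7.4 links to an error model it regards as inadequate, and that source has no randomized arms. The share of an intervention benefit explained may be biased, with direction unknown and size not computable from the Protocol. The ratios above rest entirely on assumed values. They show that the share can be understated, overstated or, if biases offset, about right.

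A reader might go further and conclude that the share will be wrong or that its intervals will be too narrow. Neither is shown: the Protocol gives no error variances, and nothing here computes interval coverage. The intention-to-treat tests and the specimen-based mediators are not affected. The point is still worth acting on because the Protocol itself describes a better source and does not carry it into section 7.5.

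**What to change.** Reword the measurement-error sentence in section 7.5 so that the source depends on the mediator:

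- **Measurements with plausibly classical error, such as assayed analytes:** keep the OS reliability sub-study as the correction source.
- **Self-reported intake with a biomarker:** use the calibrated values described in section 7.4 and carry the calibration uncertainty into the interval. Include DM arm in the calibration if the biomarker subsets contain both arms. Section 7.4 does not say which women they contain, so this must remain conditional.
- **Self-reported nutrients without a biomarker:** report the uncorrected estimate with a sensitivity range that covers arm-differential reporting. State the assumed shifts beside the results.

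The cost is the rewording, some extra analysis and somewhat wider intervals. The biomarker sub-studies have already been carried out, so the change does not in itself call for new data.

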## **7.6 Joint Analyses of Intervention Effects in the Clinical Trial and Observational Study**

The parallel nature of the CT and OS components and the OS assessment of exposures related to the interventions under test in the CT support an important opportunity to examine discrepancies between the results of these two study designs, ascertain potential reasons for these differences, and in some circumstances, use these combined analyses to refine and extend the results of the CT, as has been used in several publications already (e.g., Prentice et al, 2005, 2006b, 2008a, 2008b, 2009). In such studies, separate analyses in both the CT and OS will be conducted according to self-reported baseline prevalence of the intervention being analyzed. In fact, whenever applicable, relative risk analyses based on randomized CT comparisons will be accompanied by corresponding OS relative risk analyses. The comparability of these analyses is enhanced by the common aspects of baseline data collection procedures and outcome determination procedures in the CT and OS. Estimated relative risk functions from the two sources will take suitable account of prior "exposure" histories and of measurement error in exposure assessment. Under circumstances in which careful analyses of this type lead to substantial agreement between CT and OS results, analyses will be conducted to extrapolate the relative risk results beyond those examined in the CT, using the OS (e.g., to longer durations of treatment or to important cohort subsets). For many observational analyses, joint analyses of the CT/OS cohorts with stratification on cohort will also be a useful strategy for examining possible explanations for differences between relative risks in the CT and OS.

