## 2.1 Considerations for Follow-up of WHI Participants

Continuing high quality clinical outcome ascertainment will increase the range of scientific issues that can be examined. In particular additional follow-up will allow the WHI to address questions related to rarer health conditions and those primarily found in women of advanced age. Extended follow-up of the entire WHI cohort will contribute to the data investigators are already using to: establish stable estimates of the magnitude of risk factor impact on health in postmenopausal women; identify new risk factors; explore risk factors of uncertain status or factors which have yet to be identified; help elucidate the mechanisms underlying the excess risk of mortality at low levels of weight, cholesterol, and blood pressure; and to examine subgroups of women (for example by race, age, SES) to determine whether or not the same risk factors operate to the same degree across such subgroups. Most CVD events and deaths occur in older women, women over the age of eighty. This is the most rapidly growing demographic in the US, and WHI has one of the largest cohorts of older women, with over 30% of the 115,000 enrolled in the Extension study having reaching their ninth decade by 2009.

As envisioned, continued follow-up will also provide the basic infrastructure on which additional, high quality investigations can be supported in a cost-efficient manner. Maintaining contact with these long-standing participants and obtaining information on their health status through an efficient nationwide mechanism will create opportunities to explore related topics (e.g., biological mechanisms of disease, predictors of healthy aging) in more depth or to evaluate emerging interventions that may prevent morbidity and mortality in this increasingly important age-group at lower cost.

Additional follow-up will also allow a reliable study of the longer term health benefits and risks of the CT interventions including those that may be affected by study treatments only many years after the initiation of intervention (e.g., mortality), particularly for the hormone therapy trials.

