### **3. Study Objectives**

The primary objectives of the continuing WHI Extension Study are:

Objective 1: To study factors leading to an increased risk of CVD in older women of diverse race and ethnicity, including CHD, stroke, heart failure, atrial fibrillation, PAD, and VTE, and conversely to examine the factors that determine absence of CVD as part of successful aging.

Objective 2: To study the longer-term effects of estrogen plus progestin and estrogen alone on cardiovascular disease, cancer and fracture incidence and mortality.

Objective 3: To serve as a platform, at low incremental cost, for a new generation of prevention trials of lifestyle interventions or supplements affecting the overall health of older women.

Objective 4: To serve as a platform, at low incremental cost, for studies of the health of post-menopausal women as they age.

To achieve these objectives full outcomes ascertainment and documentation will occur annually in two important sub-cohorts of women—those in the hormone trials, plus African-American and Hispanic women—a target of 24,000 of whom 8,000 will be over age 80, and 10,000 will be racial/ethnic minorities. In addition, self-reported outcomes for the full range of health conditions will be collected annually from the entire cohort to support the same high quality documentation of their outcomes as funding permits.

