### **4.3 Outcomes of Interest**

To support the broader scientific objectives of the WHI Extension Study, some that are uniquely feasible in a very large study of older women, information on a broad range of health events and conditions will be

ascertained through both active and passive follow-up mechanisms. With the increased emphasis on heart disease and aging, several new study outcomes are now included. In most cases, outcomes will be ascertained initially through self-report (or proxy report in the case of death or incapacity). Selected self-reported outcomes will be documented and adjudicated based on study priorities and funding as described in *Table 1*.

**Medical Records Cohort (MRC):** Full outcomes ascertainment and documentation will be conducted in two important sub-cohorts of women: those in the hormone trials plus all African American and Hispanic participants.

**Self-Report Cohort (SRC):** The remaining WHI Extension Study participants will be followed with outcomes ascertainment limited to self (or proxy) report or passive follow-up sources of information unless or until funding is obtained to collect their medical records.

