**Table 1**  
**Outcomes by Study Component and Level of Information Required.**  
 A—Adjudicated medical records; S—Self/Proxy Report/Passive follow-up only;  
 L—Limited documents reviewed for capture of other events/ ICD9 coding;

Outcome	Medical Records Cohort (MRC)	Self-Report Cohort (SRC)
CARDIOVASCULAR:		
Coronary heart disease	A	S
Angina	S	S
Coronary Artery Bypass Surgery	A	S
PTCA	A	S
Heart valve problem/repair 	A	S
Aortic aneurysm 	A	S
Stroke	A	S
Transient ischemic attacks	S	S
Carotid artery disease	A	S
Heart Failure 	A	S
Atrial Fibrillation 	A	S
Venous thromboembolic disease 	A	S
Peripheral vascular disease	A	S
CANCER:		
All sites except non-melanoma skin cancer	A	A
FRACTURES:		
Hip	A	S
Other fractures	S	S
OTHER AGE-RELATED DISEASES		
Chronic obstructive pulmonary disease (COPD) 	S	S
Diabetes mellitus requiring therapy (insulin, pills, diet)	S	S
Hypertension requiring therapy	S	S
Intestinal or colon polyps or adenomas	S	S
Macular degeneration	S	S
Osteoarthritis or arthritis associated with aging	S	S
Parkinson's disease	S	S
Systemic lupus erythematosus	S	S
SOCIAL/PSYCHOLOGICAL CONDITIONS		
Moderate/severe memory problems (dementia/Alzheimer's)	S	S
OTHER		
Selected Hospitalizations for 2+ nights	L	S
Falls	S	S
Hysterectomy	S	S
Death from any cause	A	S

 - Outcome added for 2010-2015 Extension

 - Previously by self-report only

 - Originally in HT only

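### For CHD, stroke, hip fracture and similar outcomes, events from 2010 are adjudicated in all hormone-trial women but self-reported in most OS women, so Section 7.6's premise of common outcome determination fails for HT-versus-OS comparisons

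*Protocol*

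**What the plan says.** Section 7.6 plans an OS relative risk alongside each applicable randomised CT relative risk. It describes the comparability of the two as "enhanced by the common aspects of baseline data collection procedures and outcome determination procedures in the CT and OS". Where CT and OS agree substantially, the OS is then used to extrapolate beyond what the CT examined, for example to longer treatment or to subsets of women. The section allows for measurement error in exposure and for stratification on CT or OS cohort.

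Section 4.3 divides participants differently. The MRC is "those in the hormone trials plus all African American and Hispanic participants". All other women form the SRC and are "followed with outcomes ascertainment limited to self (or proxy) report or passive follow-up sources of information unless or until funding is obtained". Table 1 applies this by outcome (A adjudicated, S self-report or passive, MRC column first). CHD reads "Coronary heart disease A S", and stroke, heart failure, atrial fibrillation, VTE, peripheral vascular disease and hip fracture are coded likewise. Cancer reads "All sites except non-melanoma skin cancer A A". Section 6.3 assigns adjudicators to cardiovascular, stroke, hip-fracture and death cases in the MRC only, and Section 9.3 presents the limit on documentation as new.

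On race, Section 2.1 wants to "determine whether or not the same risk factors operate to the same degree across such subgroups", and Objective 1 in Section 3 is "To study factors leading to an increased risk of CVD in older women of diverse race and ethnicity". Sections 7.4 to 7.6 do not mention the MRC/SRC split.

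**The concern.** Hormone-trial membership alone puts a woman in the MRC. An OS woman enters it only if she is African American or Hispanic. From 2010, an HT-versus-OS comparison of an A/S outcome therefore sets adjudicated events on one side against mostly self-reported events on the other. Stratifying on CT or OS cohort does not equalise this, and the measurement-error clause covers exposure, not outcome.

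Agreement between CT and OS decides whether results are extrapolated, and disagreement is itself to be explained. A difference in ascertainment can distort either reading. In whole-cohort race comparisons, race largely decides which outcome definition a woman receives, so an apparent difference in a risk factor's effect could come from that alone.

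**Working it through.** The protocol gives no design figure for this point, so I first checked the Figure 1 counts for the 2005-2010 Extension.

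- HT women: 6,545 + 6,243 + 3,778 + 3,867 = 20,433.
- CT women not in HT: 52,176 − 20,433 = 31,743, as printed.
- Total: 52,176 + 63,230 = 115,406, as printed.

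**HT versus OS.** Inputs are the MRC target of 24,000 (Section 3) and 80% re-consent (Section 4.4), applied to the 2005-2010 counts.

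- HT women in the MRC: 0.80 × 20,433 ≈ 16,346, so 100% of continuing HT women are adjudicated.
- MRC women outside HT: 24,000 − 16,346 = 7,654.
- Continuing OS women: 0.80 × 63,230 = 50,584.
- Largest possible adjudicated share of the OS, if all 7,654 were OS women: 7,654 / 50,584 = 15%.

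Section 4.4 applies the 80% to living women under active surveillance in 2010, a count it does not give. The continuing totals here are therefore upper bounds. With the 24,000 target held fixed, fewer remaining women would raise the OS share. If 70% of the 2005-2010 enrolment continued, it would be 9,697 / 44,261 = 22%; if 90%, 5,610 / 56,907 = 10%.

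**CaD and DM.** Share also in HT, and so adjudicated whatever their race:

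- CaD: (29,862 − 16,946) / 29,862 = 12,916 / 29,862 = 43%.
- DM: 14,769 + 23,089 = 37,858, and (37,858 − 31,743) / 37,858 = 6,115 / 37,858 = 16%.

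African American and Hispanic women outside HT add to both shares, by numbers the protocol does not give. As an illustration, split the 7,654 between non-HT CT women and the OS in proportion to enrolment. Non-HT CT women, all of whom are in DM, then get 7,654 × 31,743 / 94,973 ≈ 2,558, and the OS gets 5,096. DM becomes (0.80 × 6,115 + 2,558) / (0.80 × 37,858) = 7,450 / 30,286 = 25%, and the OS 5,096 / 50,584 = 10%. That gap is small beside HT's 100% against 10%.

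**Race, whole cohort.** Section 3 expects 10,000 minority women among the 24,000. I assume these are the African American and Hispanic women.

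- Continuing women: 0.80 × 115,406 = 92,325.
- African American and Hispanic women adjudicated: 100%.
- Other women adjudicated: (24,000 − 10,000) / (92,325 − 10,000) = 14,000 / 82,325 = 17% (15-20% for 90-70% re-consent).

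**Possible effect on a hazard ratio.** Let PPV be the share of self-reported events that are true. With false positives unrelated to exposure, observed HR = HR × PPV + (1 − PPV). The protocol gives no PPV, so 0.6-0.9 is assumed. For a true HR of 1.5:

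| PPV | Observed HR, all events self-reported | Ratio to 1.5 | Observed HR, half of events adjudicated |
|---|---|---|---|
| 0.6 | 1.30 | 0.87 | 1.40 |
| 0.7 | 1.35 | 0.90 | 1.425 |
| 0.8 | 1.40 | 0.93 | 1.45 |
| 0.9 | 1.45 | 0.97 | 1.475 |

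The last column averages the all-self-report value with 1.5. It stands for a cumulative analysis in which, by assumption, half the events were adjudicated before 2010; the ratio to 1.5 is then 0.93-0.98.

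**The case against.** The sentence in Section 7.6 speaks of common aspects, not identical procedures, and some aspects are common. Form 33 goes to every woman each year (Table 2), and passive follow-up covers the whole cohort (Section 5.3). The joint CT/OS publications that Section 7.6 cites date from 2005-2009, before the split. Section 3 says the objectives will be met through full documentation in the two MRC sub-cohorts, which points to one adjudicated definition for Objective 1. The endpoint definition for each joint analysis can also be left to a statistical analysis plan. Further funding or CMS linkage might narrow the gap.

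Much of this stands, and it limits the point. It does not remove it, because the protocol offers shared outcome determination as a reason for comparability without qualification, while its own Table 1 withdraws that for post-2010 A/S outcomes in the HT-versus-OS contrast. Extra funding is conditional, and neither it nor the linkage is described as bringing endpoints to one definition.

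Three stronger readings are tempting and not supported:

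- A reader might infer that CT versus OS is the same as adjudicated versus self-reported throughout. It is not: the contrast is near complete only for HT, and cancer (A/A), angina and TIA (both S/S) escape it.
- A reader might infer that restricting to the MRC cannot rescue race comparisons. Across the whole MRC, race is partly confounded with trial membership, because every MRC woman outside HT is African American or Hispanic. Hormone-trial women of all races, however, share one adjudicated definition, and about 14,000 non-minority women in the MRC are among them.
- A reader might take 1.30-1.45 as the expected bias. It is a worst case on an assumed PPV, and Section 7.5 plans cumulative as well as post-intervention analyses of the trials.

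**Conclusion.** The point holds in a limited form. For outcomes coded A/S, Section 7.6's comparability premise fails for HT-versus-OS comparisons of events from 2010: 100% adjudicated against at most about 15% (10-22% over the re-consent range above). Whole-cohort race comparisons have the same defect, 100% against about 17%, and Sections 7.4 to 7.6 do not specify the single-definition comparison that hormone-trial women would allow.

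The mismatch follows from Section 4.3 and Table 1 and needs no assumption about self-report. The size of any bias does: it depends on the unknown validity of self-report and on the share of events after 2010. A reader might also infer that the longer-term hormone results are compromised. They are not, because both arms of each hormone trial are in the MRC, so Objective 2's randomised comparisons are unaffected. Severity is moderate.

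**What to change.** Qualify the Section 7.6 sentence so that it does not cover post-2010 events for outcomes coded A/S in Table 1. Add to Sections 7.4 and 7.6 that, for these outcomes, each CT-OS or race comparison uses one ascertainment level in both groups.

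For HT-OS comparisons, choose one of:

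- Follow-up to the end of full-cohort adjudication, only for outcomes adjudicated in the full cohort before 2010. Table 1's footnotes rule out atrial fibrillation (added for 2010-2015) and heart failure (previously self-report). VTE (originally HT only) qualifies only if full-cohort adjudication is confirmed.
- The Form 33 self-report definition for everyone. Paired self-report and adjudicated data in the MRC can estimate false positives, assuming self-report performs alike in the SRC. They say little about missed events, because Form 33 is what mainly triggers record retrieval.

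For race comparisons, use adjudicated events in hormone-trial women of all races, or self-report for everyone.

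The change is to analysis wording and needs no new data collection. Its cost is fewer events, or a less specific endpoint, in these comparisons.
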